**A non-interventional, post-authorisation safety study of patients treated
with efgartigimod alfa**

Protocol Number: ARGX-113-PASS-2208

Version: 1.0

EU PAS Register Number: Study to be registered

Protocol Approval Date: 14 December 2023

Compound: Efgartigimod alfa (VYVGART)

Sponsor

argenx BV

The information in this document is the property of argenx and is strictly confidential. Neither the document nor the information contained herein may be reproduced or disclosed outside of argenx without the prior written consent of the company

Title	A non-interventional, post-authorisation safety study of patients treated with efgartigimod alfa.
Protocol version identifier	Version 1.0
Date of last version of protocol	
European Union (EU) Post-authorisation Study (PAS) register number	To be determined
Active substance	Efgartigimod alfa (efgartigimod)
Medicinal product	VYVGART
Product reference	H005849
Procedure number	EMA/H/C/0005849/MEA002.2
Marketing authorisation holder (MAH) & license holders	argenx BV
Joint post-authorisation safety study (PASS)	No
Research question and objectives	
A non-interventional 10-year Post-Authorization Safety Study (PASS) in a post-marketing setting comparing cohorts of patients with gMG treated with efgartigimod to those treated with other MG medication, in order to estimate the incidence rates of serious infection and other safety events.
 
Primary Objective
 
 To evaluate the overall long-term safety of efgartigimod including the occurrence of serious infections in generalized myasthenia gravis (gMG) patients treated with efgartigimod compared to gMG patients not exposed to efgartigimod. 
Exploratory Objectives
 
 To evaluate the safety of efgartigimod in immunocompromised patients To evaluate the safety of efgartigimod administered to patients treated with monoclonal antibodies To evaluate the safety of efgartigimod in patients receiving live/attenuated vaccine To evaluate the safety of efgartigimod in patients with moderate to severe renal impairment
Regions and countries of study	Europe & United States (US)
Author	argenx BV

Marketing Authorization and License Holders

MAH & License holders	argenx BV [name]
MAH contact person	Mrs. [REDACTED]

Sponsor Approval

2. LIST OF ABBREVIATIONS AND DEFINITIONS OF TERMS

Abbreviation	Definition
ADL	Activities of Daily Living
AE	Adverse Event
AChE	Acetylcholinesterase
AChR	Acetylcholine Receptor
ATC	Anatomical Therapeutic Chemical
CDC	Centre for Disease Control and Prevention
CFR	Code of Federal Regulations
CI	Confidence Interval
CRA	Clinical Research Associate
CRF	Case Report Form
CRO	Contract Research Organisation
CTCAE	Common Terminology Criteria for Adverse Events
eCRF	Electronic Case Report Form
eGFR	Estimated Glomerular Filtration Rate
EDC	Electronic Data Capture
ENCePP	European Network of Centres for Pharmacoepidemiology and Pharmacovigilance
EU	European Union
FcRn	Fragment crystallisable Receptor
GDPR	General Data Protection Regulation
gMG	Generalised Myasthenia Gravis
HCP	Healthcare Professional
ICF	Informed Consent Form
IEC	Independent Ethics Committee

Abbreviation	Definition
IRB	Institutional Review Board
Ig	Immunoglobulin
IV	Intravenous
IVIg	Intravenous Immunoglobulins
LRP4	Lipoprotein Receptor-Related Protein 4
MedDRA	Medical Dictionary for Regulatory Activities
MAH	Marketing Authorisation Holder
MG	Myasthenia Gravis
MuSK	Muscle-Specific Tyrosine Kinase
MyaReg	Deutsches Myaesthenie Register
PAS	Post-Authorisation Study
PASS	Post-Authorisation Safety Study
PLEX	Plasmapheresis/Plasma Exchange
PRAC	Pharmacovigilance Risk Assessment Committee
PT	Preferred Term
RMP	Risk Management Plan
SD	Standard Deviation
SAE	Serious Adverse Event
SAP	Statistical Analysis Plan
SMQ	Standardised MedDRA Query
SOC	System Organ Class
UK	United Kingdom
US	United States
WHO	World Health Organisation

3. RESPONSIBLE PARTIES

Sponsor	argenx BV
Contract research organization	United BioSource LLC

4. ABSTRACT

Title

A non-interventional, post-authorisation safety study of patients treated with efgartigimod alfa.

Rationale and Background

Myasthenia gravis (MG) is an autoimmune disease caused by immunoglobulin G (IgG) antibodies against postsynaptic antigens at the neuromuscular junction. IgG autoantibodies impair neuromuscular transmission by binding to acetylcholine receptors (AChR), muscle-specific tyrosine kinase (MuSK) or low-density lipoprotein receptor-related protein 4 (LRP4).

Myasthenia gravis can be classified into various subgroups based upon antibody status, age of onset and/or degree of muscle involvement. Ocular symptoms are the most common initial presentation of disease and about two thirds of ocular MG patients progress to generalised MG (gMG) within the first 2-3 years ([Anil 2020](#)).

Efgartigimod alfa (efgartigimod) is a human IgG1 antibody fragment engineered for increased affinity to the neonatal Fragment crystallisable Receptor (FcRn). Efgartigimod binds to FcRn, resulting in the reduction of circulating IgG including IgG autoantibodies. Efgartigimod does not affect the levels of other immunoglobulins (IgA, IgD, IgE, or IgM), or those of albumin.

In the United States (US), efgartigimod is approved for the indication of gMG in adult patients who are AChR antibody positive and in the European Union (EU) it is approved as an add-on to standard therapy for the treatment of adult patients who are AChR antibody positive.

The purpose of this study is to evaluate the important potential risks and missing information as set out in the EU Risk Management Plan (RMP) in a larger patient population for a longer duration than in clinical trials and under conditions of normal clinical practice.

Research Question and Objectives

A non-interventional 10-year Post-Authorization Safety Study (PASS) in a post-marketing setting comparing cohorts of patients with gMG treated with efgartigimod to those treated with other MG medication, in order to estimate incidence rates of serious infection and other safety events.

Primary objective

- To evaluate the overall long-term safety of efgartigimod including the occurrence of serious infections in gMG patients treated with efgartigimod compared to gMG patients not exposed to efgartigimod.

Exploratory objectives

- To evaluate the safety of efgartigimod in immunocompromised patients.
- To evaluate the safety of efgartigimod administered to patients treated with monoclonal antibodies.
- To evaluate the safety of efgartigimod in patients receiving live/attenuated vaccine.
- To evaluate the safety of efgartigimod in patients with moderate to severe renal impairment

Study Design

This is a non-interventional, prospective, post authorisation safety study.

Patients with gMG who are expected to start treatment with efgartigimod at enrolment or are within their first cycle of efgartigimod at enrolment will be eligible to enrol into the efgartigimod cohort. Patients with gMG who have not been exposed to efgartigimod and for whom it is not planned to start treatment with efgartigimod at enrolment will be eligible to enrol into the non-efgartigimod cohort.

Enrolment of patients will be over at least a 5-year period. The follow up of patients will continue for 5 years from the time the last patient has been enrolled. Patients will be followed up regardless of whether they continue or discontinue efgartigimod.

In order to minimise heterogeneity between the two cohorts, patients in the efgartigimod cohort will be matched at enrollment with a patient in the non-efgartigimod cohort for the following criteria:

- Age (± 5 years)
- Myasthenia Gravis -Activities of Daily Living (MG-ADL) score (0-5, 5-9, and >9) ([Wolfe, 1999](#))
- Region (within EU and within US)

Population

Inclusion Criteria (efgartigimod cohort)

1. Patients diagnosed with gMG who are expected to start commercial efgartigimod at enrolment or who are within their first cycle of efgartigimod at enrolment
2. Have provided appropriate written informed consent

Inclusion Criteria (non-efgartigimod cohort)

1. Patients diagnosed with gMG who have not been exposed to efgartigimod and for whom it is not planned to start treatment with efgartigimod at enrolment
2. Have provided appropriate written informed consent

Exclusion Criteria

None

Data Sources

Data will be extracted from the patient's medical records by site personnel and entered into the electronic data capture (EDC) on an ongoing basis.

Study Size

It is anticipated that 340 patients will be enrolled in each cohort as per the inclusion criteria above.

Data Analysis

Categorical endpoints will be summarised using counts and percent; continuous endpoints will be summarised using mean, standard deviation, median, minimum and maximum values. Statistical analysis will be mainly descriptive in nature using metrics such as incidence proportion, exposure-adjusted incidence rate, confidence intervals, etc. Details of the analysis plan will be specified in the Statistical Analysis Plan (SAP).

Milestones

Milestones are estimated and are dependent upon the date of the Pharmacovigilance Risk Assessment Committee (PRAC) approval of the protocol. Patient enrolment will begin within 6 months of PRAC approval, and the end of data collection will be 10 years after the start of data collection. Interim reports will be submitted in years 4 and 8 after the start of data collection, with study progress reports submitted annually in the intervening years. The final study report is estimated to be submitted 1 year after the end of data collection.

5. AMENDMENTS AND UPDATES

None

6. MILESTONES

Milestone	Planned date
Submission of study protocol for Pharmacovigilance Risk Assessment Committee (PRAC) approval	28 November 2022
Approval of study protocol by PRAC	To Be Determined
Registration in European Union Post-Authorisation Study (EU PAS) Register*	At time of PRAC approval of protocol
Start of data collection/first patient enrolled*	Within 6 months after PRAC approval
Last patient enrolled*	5 years after start of enrolment
End of data collection*	10 years after start of data collection
Study progress report*	Year 1 after start of data collection
Study progress report*	Year 2 after start of data collection
Study progress report*	Year 3 after start of data collection
Interim report of study results*	Year 4 after start of data collection
Study progress report*	Year 5 after start of data collection
Study progress report*	Year 6 after start of data collection
Study progress report*	Year 7 after start of data collection
Interim report of study results*	Year 8 after start of data collection
Study progress report*	Year 9 after start of data collection
Study progress report*	Year 10 after start of data collection
Final report of study results*	Estimated 1 year after end of data collection

* timelines may change depending upon Pharmacovigilance Risk Assessment Committee (PRAC) protocol approval date

7. RATIONALE AND BACKGROUND

Myasthenia gravis (MG) is an autoimmune disease caused by immunoglobulin G (IgG) antibodies against postsynaptic antigens at the neuromuscular junction. IgG autoantibodies impair neuromuscular transmission by binding to acetylcholine receptors (AChR), muscle-specific tyrosine kinase (MuSK) or low-density lipoprotein receptor-related protein 4 (LRP4).

From an immunological point of view, approximately 80% of patients with MG have detectable antibodies against AChR. These patients are known as AChR antibody positive.

The estimated prevalence rate for MG is 77.7 per million persons (range 15–179) and the estimated incidence rate is 5.3 per million person-years (range 1.7–21.3) [Carr 2010].

MG occurs in both genders, at all ages, and in all races [Carr 2010, McGrogan 2010]. The most common age of MG onset is between 20 and 40 years. In this age group, about 60% of patients are women. In older age groups, men are affected more often, and the disease is often misdiagnosed. As a result, there is a bimodal distribution with a female predominance in the second to third decade of life and male predominance in the sixth to eighth decade [Philips 2004, Spillane 2012].

MG can be classified into various subgroups based upon antibody status, age of onset and/or degree of muscle involvement. Ocular symptoms are the most common initial presentation of disease and about two thirds of ocular MG patients progress to generalised MG (gMG) within the first 2-3 years (Anil 2020).

A considerable variation exists in the management of gMG, and treatment is not standardized. Current treatment options include acetylcholinesterase (AChE) inhibitors, and long-term immune therapies with immunosuppressive agents such as corticosteroids, azathioprine, cyclosporine, and mycophenolate, but tacrolimus, methotrexate, and cyclophosphamide are also used. There is no consensus on the choice of immunosuppressive agent. Thymectomy is also a treatment option for patients with generalised MG. Monoclonal antibodies such as eculizumab or rituximab are used for more refractory cases [Vyvgart EPAR].

Short term immune therapies such as plasmapheresis/plasma exchange (PLEX) and intravenous immunoglobulins (IVIg) are typically used for treatment of severe exacerbations of gMG [Vyvgart EPAR].

With the exception of AChE inhibitors, the complement inhibitor eculizumab, and a liquid formulation of azathioprine, which have received regulatory approval in Europe for the treatment of gMG, all other existing therapies are used off-label [Vyvgart EPAR].

In the United States (US), efgartigimod is approved for the indication of gMG in adult patients who are AChR antibody positive and in the EU it is approved as an add-on to standard therapy for the treatment of adult patients who are AChR antibody positive.

The recommended dose of efgartigimod is 10 mg/kg as a 1-hour intravenous infusion to be administered in cycles of once weekly infusions for 4 weeks. Subsequent treatment cycles are administered according to clinical evaluation. The frequency of treatment cycles may vary by patient.

In the EU Risk Management Plan (RMP) for efgartigimod, serious infections, is considered to be an important potential risk. As efgartigimod induces a transient lowering in IgG levels, there is a potential

risk for infections associated with the lowered IgG levels. In the randomized placebo-controlled study of 167 patients ARGX-113-1704, 84 patients with gMG were exposed to efgartigimod and the most frequently observed adverse reactions were upper respiratory infections (10.7% in the efgartigimod patients and 4.8% in the placebo patients) and urinary tract infections (9.5% in the efgartigimod patients and 4.8% in the placebo patients). In the patients who received efgartigimod, these events were \leq Grade 2 according to the Common Terminology Criteria for Adverse Events (CTCAE). Overall, treatment emergent infections were reported in 46.4% of patients treated with efgartigimod and 37.3% of patients treated with placebo. The frequency of infections in the efgartigimod treated patients did not increase with repeated cycles of treatment. There were no serious infections or opportunistic infections in the efgartigimod treated patients. This study will evaluate the occurrence of serious infections in gMG patients treated with efgartigimod in the real world setting under conditions of normal clinical practice compared to gMG patients who are not treated with efgartigimod.

During clinical development of the IV formulation, in the efgartigimod phase 3 placebo-controlled 26 week clinical study, ADAPT, there were 2 reported neoplasm events, 1 (1.2%) in the efgartigimod treatment arm and 1 (1.2%) in the placebo treatment arm.

During the ADAPT open-label extension study, ADAPT+, all patients received efgartigimod. Up until the data analysis cut-off date of 01February2021, for a mean duration of exposure of 363 days, there were 7 (5.0%) patients with a reported neoplasm: 3 (4.1%) in the efgartigimod – efgartigimod group and 4 (6.1%) in the placebo to efgartigimod group. The maximum number of cycles completed as of the 01February2021 database cut-off was 10 cycles. All malignant neoplasms were assessed as not related to efgartigimod by the investigator. The safety data reported in the efgartigimod studies in MG patients and available data for other IgG reducing agents or treatments do not suggest a correlation between IgG reduction and an increased risk of developing cancer. The etiology of cancer is complex. Literature on cancer immune responses does not suggest that a selective reduction of IgG, without lowering other immunoglobulin isotypes such as IgM, or affecting cell-mediated immunity, would generally increase the risk of developing cancers or have an effect on factors that promote carcinogenesis. Efgartigimod lowers IgG levels with no relevant decrease in all the other types of antibodies (IgA, IgD, IgE, IgM) or in albumin levels. Immunosuppressants, which patients with gMG take concomitantly with efgartigimod alfa, can impair the immune response to cancer. Regardless, malignancy has been included as an important potential risk in the EU RMP. Therefore, malignant events will be collected as events of interest throughout the PASS study.

The long-term safety of efgartigimod is considered to be missing information. As of 01 Feb 2021, the maximum duration of treatment with efgartigimod and follow-up was 721 days with a median duration of 451 days, in patients who received efgartigimod intravenously (IV) 10 mg/kg. Overall, the duration of treatment combined with follow-up was at least 6 months for 143 patients, at least 12 months for 118 patients, and at least 18 to <24 months for 33 patients. No clinically significant cumulative toxicities have been identified.

This study will evaluate the overall long-term safety of efgartigimod including the occurrence of serious infections in gMG patients treated with efgartigimod compared to gMG patients not exposed to efgartigimod over a maximum 10 year period under conditions of normal clinical practice.

In the EU RMP, use of efgartigimod in immunocompromised patients, in patients with moderate to severe renal impairment, in patients taking concomitant monoclonal antibodies and in patients receiving

live/attenuated vaccines is considered to be missing information as efgartigimod has not been studied in these patient populations. This post authorisation safety study will include these patient populations according to normal clinical practice. If these patients are enrolled into the study, the safety of efgartigimod will be assessed in these patient populations.

8. RESEARCH QUESTION AND OBJECTIVES

A non-interventional Post-Authorization Safety Study (PASS) in a post-marketing setting comparing cohorts of patients with gMG treated with efgartigimod to those treated with other MG medication for 10 years, in order to estimate incidence rates of serious infection and other safety events.

Primary Objective

- To evaluate the overall long-term safety of efgartigimod including the occurrence of serious infections in gMG patients treated with efgartigimod compared to gMG patients not exposed to efgartigimod.

Exploratory Objectives

- To evaluate the safety of efgartigimod in immunocompromised patients
- To evaluate the safety of efgartigimod administered to patients treated with monoclonal antibodies
- To evaluate the safety of efgartigimod in patients receiving live/attenuated vaccine
- To evaluate the safety of efgartigimod in patients with moderate to severe renal impairment

9. RESEARCH METHODS

9.1 Study Design

This is a non-interventional, prospective, post authorisation safety study.

Patients with gMG who are expected to start treatment with efgartigimod at enrolment or are within their first cycle of efgartigimod at enrolment will be eligible to enrol into the efgartigimod cohort. Patients with gMG who have not been exposed to efgartigimod and for whom it is not planned to start treatment with efgartigimod at enrolment will be eligible to enrol into the non-efgartigimod cohort. It is anticipated that 340 patients will be enrolled in each cohort.

Patients will be treated and observed according to normal clinical practice. Participation in this study does not limit the physicians` clinical decision making as to the most appropriate treatment for the patient during the course of the study. No visits or investigations outside of normal clinical practice will be required. The enrolled patients will be followed prospectively until end of study participation, loss to follow up, consent withdrawal, or death, whichever comes first. All adverse events (AEs) will be collected throughout the duration of the study.

Enrolment of patients will be over a 5-year period. The follow up of patients will continue for 5 years from the time the last patient has been enrolled. Patients will be followed regardless of whether they continue or discontinue efgartigimod. Assuming a 5-year enrolment period this will allow for a maximum of 10 years of follow-up and a minimum of 5 years. A patient will be considered to be an efgartigimod exposed patient if he/she has received at least one dose of efgartigimod.

In order to minimise heterogeneity between the two cohorts, patients in the efgartigimod cohort will be matched at enrollment with a patient in the non-efgartigimod cohort for the following criteria:

- Age (\pm 5 years)
- Myasthenia Gravis -Activities of Daily Living (MG-ADL) score (0-5, 5-9, and >9) ([Wolfe, 1999](#))
- Region (within EU and within US)

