9.2.1 Selection of Study Population

Patients with gMG who are expected to start treatment with efgartigimod at enrolment or are within their first cycle of efgartigimod at enrolment will be eligible to enrol into the efgartigimod cohort. Patients with gMG who have not been exposed to efgartigimod and for whom it is not planned to start

treatment with efgartigimod at enrolment will be eligible to enrol into the non-efgartigimod cohort.

Physicians participating in the study will be instructed to invite all patients who meet study eligibility criteria to enrol until the enrolment period is closed.

Inclusion Criteria (efgartigimod cohort)

1. Patients diagnosed with gMG who are expected to start commercial efgartigimod at enrolment or who are within their first cycle of efgartigimod at enrolment
2. Have provided appropriate written informed consent

Inclusion Criteria (non-efgartigimod cohort)

3. Patients diagnosed with gMG who have not been exposed to efgartigimod and for whom it is not planned to start treatment with efgartigimod at enrolment
4. Have provided appropriate written informed consent

Exclusion Criteria

None

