gMG treatments at or following enrollment (excluding efgartigimod)	
 Drug name, dose, start and stop dates 
 Acetylcholinesterase inhibitors Corticosteroids Other Immunosuppressants (specify) Monoclonal antibodies (specify) Plasmapheresis/plasma exchange acute Plasmapheresis/plasma exchange chronic IVIg therapy acute IVIg therapy chronic Other 	✓	✓

Category	Variables	Baseline	Follow up
Efgartigimod treatment	
 • Date of administration • Reason for interruption during cycle of treatment • Reason for permanent discontinuation whilst on study 	✓	✓
Other comedications at or following enrollment for conditions other than gMG	
 • Drug name, start and stop dates • Indication 	✓	✓
Live/attenuated vaccinations 2 months prior to enrollment to 2 months after last Vyvgart dose	
 • Live/attenuated vaccine 
 ○ Vaccine ○ Date 	✓	✓
Adverse Events (AEs)/Serious Adverse Events (SAEs)	
 • AEs, SAEs 		✓
Events of interest	See Table 2		✓

*All variables will be collected ONLY if available as part of routine clinical practice

A patient will be considered to be an efgartigimod exposed patient if he/she has received at least one dose of efgartigimod.

Additionally, taking into account the variable follow up time and time interval between cycles, the following will be measured for efgartigimod:

- Number of administrations per year
- Total duration of the exposure
- Total number of administrations

The exposure time window of efgartigimod is 56 days +/-3 days after the last dose.

Events of interest in this study will be pre-specified as per [Table 2](#) below.

Table 2: Pre-specified events of interest

Event of interest	Definition	Measurement
Serious infection	Any serious adverse event coded to the Medical Dictionary for Regulatory Activities (MedDRA) System Organ Class (SOC) of Infection and Infestation. See Section 11 for definition of Serious.	Proportion of patients who report serious infections during the course of the study in the efgartigimod treated cohort compared to the non-efgartigimod cohort. Incidence rate of serious infections per patient-years exposed in the efgartigimod treated cohort compared to the non-efgartigimod cohort.

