9.7 Data Analysis

The Full Population will be all patients enrolled.

The Safety Population will include all patients enrolled who have taken at least one dose of efgartigimod for the efgartigimod cohort and all patients enrolled into the non-efgartigimod cohort. All analysis will be based on the Safety Population.

Unless otherwise specified, categorical endpoints will be summarised using counts and percent; continuous endpoints will be summarised using mean, standard deviation, median, minimum and maximum values. Statistical analysis will be mainly descriptive in nature using metrics such as

incidence proportion, exposure-adjusted incidence rate, confidence intervals, etc. Details of the analysis plan will be specified in the Statistical Analysis Plan (SAP).

Primary objective

Descriptive statistics will be used to summarise the long-term safety of efgartigimod, including the occurrence of events of serious infections, in gMG patients treated with efgartigimod compared to gMG patients not exposed to efgartigimod. The number and percentage of patients with AEs/SAEs will be presented. The rate per person-year exposure with a 95% CI will be constructed using asymptomatic normal approximation.

Although no formal hypothesis will be tested in the study, statistical models will be used to test the difference of incidence between treatment cohorts (efgartigimod vs. comparator). Two base models which are widely used to model incidence proportion and incidence rate adjusted by potential confounders will be used:

1. To model incidence proportions, a logistic regression model will be used including patients with event vs. patients without event as the response variable and treatment group and country as covariates.
2. To account for varied follow-up time, a Cox regression model will be used with time to the first occurrence of event for each patient as the response variable, treatment group and country as covariates .

Countries with small sample sizes will be combined with other countries based on the geographic locations. Other covariates may be added to the above base models as described below.

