Balance of the baseline measures, including age, MG-ADL score and region matched at enrollment and other demographic and disease characteristics, will be assessed. The imbalanced measures which are considered to be potential confounders based on clinical judgement will be added to the above base models as covariates. If a large number of imbalanced potential confounders are identified after the enrollment is complete, a propensity score method will be applied instead. More details will be given in the SAP.

Subgroup analyses will be performed using descriptive statistics on the subset of patients who remained on efgartigimod throughout the duration of the PASS. In addition, subgroup analyses of treatment cycle per year or administration per year (four administrations in one cycle if not interrupted), subgroup analyses of time since the last administration of efgartigimod prior to the event occurrence in intervals of every 4 weeks will be performed, and subgroup analysis of patients using efgartigimod as add-on or single treatment will be performed if sample size allows. Since one patient may have multiple same events with different time to the last administration, one patient may be assigned to multiple time intervals.

Events of Interest

Statistical analysis of malignancy and other events of interest will follow the same method as those for serious infections

Exploratory objectives

Descriptive statistics will be used to summarise the long-term safety of efgartigimod for specific subgroups. The number and percentage of patients with AEs/SAEs will be presented. The rate per person-year exposure with a 95% CI will be constructed using asymptomatic normal approximation. This will be done for the following subgroups:

- immunocompromised patients and immunocompetent patients.
- patients treated with monoclonal antibodies and patients not treated with monoclonal antibodies.
- patients who have received live/attenuated vaccine and patients who have not received live/attenuated vaccine.
- patients with moderate to severe renal impairment and patients with normal renal function or mild renal impairment.

Missing values

No imputation will be applied to occurrence of serious infection, malignancy or other safety events.

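### Efgartigimod patients enter at or just after a treatment start, comparators at any point of their treatment, and neither the matching nor the base models align the two on recent treatment start

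*Protocol*

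**What the plan says.** Protocol 9.1 takes into the efgartigimod cohort "Patients with gMG who are expected to start treatment with efgartigimod at enrolment or are within their first cycle of efgartigimod at enrolment". For the comparator it takes "Patients with gMG who have not been exposed to efgartigimod and for whom it is not planned to start treatment with efgartigimod at enrolment". Section 9.2.1 repeats both rules and lists no exclusion criteria. Section 8 describes the study as "comparing cohorts of patients with gMG treated with efgartigimod to those treated with other MG medication for 10 years".

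Under 9.1, "patients in the efgartigimod cohort will be matched at enrollment with a patient in the non-efgartigimod cohort for the following criteria"; the criteria are age within 5 years, MG-ADL band and region. Section 9.7 gives two base models, a logistic regression and a Cox regression on time to first event, each with "treatment group and country as covariates". It continues: "The imbalanced measures which are considered to be potential confounders based on clinical judgement will be added to the above base models as covariates". A propensity score replaces this if many potential confounders are imbalanced.

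Table 1 in 9.3 records gMG treatments from diagnosis to enrolment with name, start date and stop date. For treatments at or after enrolment it records "Drug name, dose, start and stop dates". Past infections are a baseline variable.

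**The concern.** Time zero means different things in the two cohorts. For an efgartigimod patient it is a decision to add or change treatment. For a comparator it is whenever the patient was invited, which may be years into an unchanged regimen. If the months after any new gMG treatment carry more serious infections, whether from the treatment or from the disease activity that prompted it, that early excess falls systematically on the efgartigimod side. The Cox model would attribute it to treatment group.

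Serious infection is the named event in the primary objective, and 9.7 uses models to test the difference in incidence. What is at stake is how a positive finding would be read after ten years: as a risk of the drug, or partly as a consequence of having just started something new.

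**Working it through.** **Entry rules and alignment.**

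| Feature | Efgartigimod | Comparator |
|---|---|---|
| Treatment event at entry | start, or within first cycle | none required |
| Matched on (9.1) | age, MG-ADL band, region | same |
| Base-model terms (9.7) | treatment group, country | same |
| Term for recent treatment start | none | none |

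Two patients in the same MG-ADL band can differ entirely in whether treatment has just changed. Time since last treatment start is not a Table 1 variable. It can be derived from the start dates, but nothing in the protocol says that it will be. Section 9.9 discusses severity and heterogeneous treatments, not new versus ongoing users. The ENCePP checklist answers No on measuring confounding (7.1) and on information bias, whose examples include time-related bias (7.3).

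**The plan's own figure.** Inputs from 9.5: 20% versus 31%, 270 per arm, two-sided 0.05, normal approximation. The mean proportion is 0.255.

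- SE0 = √(2 × 0.255 × 0.745 / 270) = 0.0375
- SE1 = √((0.31 × 0.69 + 0.20 × 0.80) / 270) = 0.0372
- Power = Φ((0.11 − 1.96 × 0.0375) / 0.0372) = 83.7% (84.0% unpooled); the protocol states 84%. Reproduced.

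The point changes none of the sample-size figures. It concerns bias.

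**Illustration of size.** Assumptions, not in the documents: no drug effect; comparators at a constant hazard giving 20% over T years; starters' hazard multiplied by k for the first m years; no covariate adjustment.

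Starters' risk = 1 − 0.8^(1 + (k − 1)m/T)

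Chance of two-sided p<0.05 = Φ((d − 1.96·SE0)/SE1) + Φ((−d − 1.96·SE0)/SE1), where d is the risk difference.

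- k = 2, m = 1, T = 5: risk 1 − 0.8^1.2 = 23.5%, d = 0.0349, both SEs about 0.0355. 16.4% + 0.2% = about 17%.
- k = 2, m = 1, T = 10: risk 1 − 0.8^1.1 = 21.8%, d = 0.0177, both SEs about 0.0350. 7.3% + 0.7% = about 8%.

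| T (years) | k | m (years) | Starters' risk | Average hazard ratio | Chance of p<0.05 |
|---|---|---|---|---|---|
| 5 | 1.5 | 0.5 | 20.9% | 1.05 | 6% |
| 5 | 2 | 1 | 23.5% | 1.20 | 17% |
| 5 | 3 | 1 | 26.8% | 1.40 | 47% |
| 7.5 | 2 | 1 | 22.4% | 1.13 | 10% |
| 10 | 2 | 1 | 21.8% | 1.10 | 8% |

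The nominal figure is 5%. Nearly all of the increase is in the direction of an apparent excess on efgartigimod. An early effect is diluted by long follow-up. The illustration also treats every comparator as not recently started; any who were would narrow the gap.

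**Precision of a restricted comparison.** Suppose one comparator in five had recently started a treatment (assumption). Then 0.20 × 270 = 54 remain. For 31% versus 20% with 270 versus 54, power is about 35% (pooled) to 43% (unpooled), against the stated 84%.

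**The case against.** The plan is not bare here. MG-ADL matching aligns current symptom burden in part. Section 9.7 commits to checking balance on other demographic and disease characteristics, and to adjusting for imbalanced confounders or using a propensity score. The choice of derived covariates is ordinarily left to the SAP, which is not at hand. Section 9.9 concedes that sicker patients are likely to receive efgartigimod and that interpretability is limited. The objective is explicitly against unexposed patients, and 9.5 calls the analysis descriptive and exploratory.

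Much of this stands, and it limits the point to an improvement. It does not remove it: the entry rules are fixed in the protocol, the balance check does not commit to deriving recent treatment start, and severity at entry is a related but different matter.

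A reader might infer three stronger things that the documents do not support:

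- **Comparators are survivors of stable regimens.** Entry does not require continued use of anything. A patient who stopped a drug because of infection remains eligible. In the EU efgartigimod is an add-on (section 7), so many starters also carry long-standing background treatment.
- **The false-positive rate is 20% to 32%.** Those figures arise if 80% of comparators are long-standing users with a hazard of 0.75 or 0.67 of starters' throughout follow-up (comparator risk 16.3% or 15.1% against 20%). Neither the share nor a permanent difference has a source in the protocol, and a permanent difference is not an early-period effect.
- **The primary comparison cannot separate drug risk from treatment start at all.** The dates needed for a partial separation are listed for collection.

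**Conclusion.** The asymmetry is real and follows from the entry criteria in 9.1 and 9.2.1. The matching and base models do not align the cohorts on recent treatment start, and 9.9 does not mention it. An excess of serious infections could partly reflect having just started a new treatment.

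The size cannot be determined from the documents. Under the assumed early hazards above it runs from negligible (0.9 percentage points, 6% chance of p<0.05) to 6.8 points (47%), against the 10 to 11 points for which 9.5 quotes power of at least 80%. A doubled hazard for one year gives 3.5 points at 5 years and 1.8 at 10. All these figures assume no drug effect and no adjustment, so the conditional adjustment in 9.7 could reduce them. This is a worthwhile, inexpensive strengthening of the primary comparison, not a flaw that invalidates it.

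**What to change.** **In 9.7:**

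1. Derive for each comparator the time from the last start of a new gMG immunotherapy to enrolment, using the Table 1 start dates. Define it by new starts, not dose escalations, because dose is not listed for treatments before enrolment.
2. Keep the all-comparator Cox model. Pre-specify beside it, as a sensitivity analysis, a comparison restricted to comparators who started a new gMG immunotherapy within a fixed window before or at enrolment. Set the window before outcomes are examined.
3. In the all-comparator model, include infection history and number of gMG treatment starts in the prior year as fixed baseline covariates, whether or not they appear imbalanced. Leave the efgartigimod start itself out of the count.
4. Report both estimates with confidence intervals. Do not make a conclusion of increased risk conditional on their agreement: that would let a comparison with perhaps 35% to 43% power veto a safety signal.

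**In 9.9:** name the difference between starting a treatment and being at any point of one as a source of bias, separately from severity.

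**Cost:** protocol and SAP wording, with no change to enrolment and no new data items, since start dates and past infections are already in Table 1. They are collected only where routine records hold them, so some will be missing. The restricted comparison is smaller and less precise, and it breaks the enrolment matching, so it needs covariate adjustment, at least for the matching factors. Capturing dose escalation before enrolment would need an added eCRF field.
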